2.3 Sample Size

The sample size was calculated using Morgan and Case's formula with the following set-up: type I error of 0.05, power of 0.90, 1-to-1 random allocation, and variance ratio of 0.44, using a conservative assumption for the compound symmetry correlation structure. A large effect size (Cohen's d) of 0.80 was determined based on the pooled effect sizes derived from our previous study and a recent RCT. Therefore, a minimum sample size of 30 participants will be required in this pilot RCT to test for 2×3 mixed design analysis of covariance (i.e., the number of two groups with three repeated measurements, adjusted for individual differences in baseline assessments). Allowing for an attrition rate of 40% that was observed in the previous study, a total of 50 parent-child dyads (25 in each group) will be recruited.

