2.7.2.3 Initial Efficacy of OPC

2.7.2.3.1 Primary Outcome Measures

Canadian Occupational Performance Measure (COPM). The COPM will be used to measure parents' perceptions of children's participation in specific community activities. This measure is selected for use because it can identify individualized problems in participation in occupations and then help to formulate goals related to child participation through semi-structured interviews. In the interview, parents are further prompted to rate their child's performance and their satisfaction with the current status on a 10-point Likert scale (1 = *not good/satisfied at all* and 10 = *optimal performance/satisfaction*). High scores indicate greater children's participation performance and parents' satisfaction. In this pilot RCT, we propose that parents' identified goals will not be limited to the community participation but will also be extended to other life areas. An adequate internal consistency (Cronbach's $\alpha = 0.73$ – 0.88) of the COPM has been reported. The prioritized problems using the COPM in parents of children with disabilities were also found to be corresponding with specific items in the Pediatric Evaluation of Disability Inventory, demonstrating construct validity of the COPM.

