Young Children's Participation and Environment Measure (YC-PEM). The YC-PEM will be used to capture children's overall community participation patterns. This measure is selected because it is a parent report questionnaire that can be used for young children with various disabilities. The YC-PEM also has a community section that includes 11 participation items across four broad categories of neighbourhood and community outings, classes and groups, community-sponsored activities, and recreational activities and trips. In each item, parents are asked to rate: (a) how often their child has participated in the past four months using an 8-point Likert scale (0 = *never* and 7 = *once or more each day*); (b) how involved the child is during participation using a 5-point Likert scale (1 = *not very involved* and 5 = *very involved*); and (c) parental desire for change in the child's participation (yes/no and, if yes, six nominal options for the type of desired change can be selected). Total scores are generated by averaging all items in the participation frequency and involvement dimensions. High scores indicate greater children's participation frequency and involvement. The YC-PEM participation scale has acceptable internal consistency ($\alpha = 0.64$ – 0.78) and test-retest reliability (intraclass correlation coefficients [ICC] = 0.82–0.89). Moreover, it demonstrates known-group validity between children with and without disabilities and convergent validity by correlating with functional performance of children with disabilities.

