To evaluate the initial efficacy of OPC on the primary and secondary outcomes, we will use the repeated-measures analysis of covariance (ANCOVA) by controlling for baseline variability at time 0 as well as the variations in treatment dosage and delivery format (e.g., in person or tele-format). That is, the repeated-measures ANCOVAs will be used to compare the change in the scores of outcome measures across the three time points (at times 1, 2, and 3) by controlling for baseline differences and treatment variations. For participation goals identified by parents in the COPM, only community-related participation goals will be targeted for analysis. Principles of intent-to-treat analysis will be applied and, if participants withdraw after the coaching/consultation sessions, their data for subsequent time points will be imputed by carrying the last assessment forward. Post-hoc analyses using the Schffé method will be performed when the main comparison results are significant. Statistical significance will be set at $p < 0.05$. Estimates of effect sizes with 95% confidence intervals will be calculated for each outcome measure.

TABLE 1: A priori success criteria to assess the feasibility of the trial

	Definition	Success criteria
Recruitment	Percentage of eligible families agreeing to participate in the study	$\geq 20\%$ recruitment response rate achieved
Retention	Percentage of participants who complete the trial	$\geq 60\%$ retention rate achieved (i.e., completion of all assessments)
Adherence	Percentage of coaching sessions attended by parents in the intervention group	$\geq 75\%$ adherence rate achieved, based on our previous research of similar duration (42)
Blinding success	Percentage of parents who guess treatment allocation correctly after the study	50% based on the guess of treatment by chance (50/50)
Fidelity	Degree to which the OPC is implemented by coaches as intended	$\geq 80\%$ fidelity on the OPC Fidelity Measure Version 3.0 in four selected session per coach

Note: The OPC Fidelity Measure Version 3.0 consists of 18 items across five domains: relationship, goal, reflection, analysis and action, client response, and distinguishing. Each item is rated on a 3-point Likert scale (1 = *low* and 3 = *high*). The percentage score will be calculated by dividing the total score by the possible maximum score. Higher percentage scores indicate higher fidelity, and the cut-off of sufficient fidelity of OPC per session is set at 80%.

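### The trial is sized for one test at 0.05, but two primary instruments yield four scores, each tested at 0.05 with no lead score, adjustment or success rule

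*Combined protocol and SAP*

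**What the plan says.** Section 2.3 (Sample Size) sets a "type I error of 0.05, power of 0.90, 1-to-1 random allocation, and variance ratio of 0.44". It uses one effect size, a Cohen's d "of 0.80 was determined based on the pooled effect sizes derived from our previous study and a recent RCT", and concludes that "a minimum sample size of 30 participants will be required in this pilot RCT". The test being sized is one 2×3 mixed-design ANCOVA adjusted for baseline. The outcome it applies to is not named. Allowing for 40% attrition, 50 dyads are to be recruited.

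Section 2.7.2.3.1 (Primary Outcome Measures) lists two instruments side by side:

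- On the COPM, parents rate the child's performance and "their satisfaction with the current status on a 10-point Likert scale".
- On the YC-PEM, "Total scores are generated by averaging all items in the participation frequency and involvement dimensions".

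No composite is defined within or across the two instruments.

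Section 2.8 (Data Analysis) applies repeated-measures ANCOVAs to the primary and secondary outcomes over times 1, 2 and 3, adjusting for time 0 and for treatment variations. It then states: "Statistical significance will be set at" p < 0.05. The only multiple-comparison method it names is Scheffé's, used post hoc once a main comparison is significant. Effect sizes with 95% confidence intervals are planned for every outcome measure.

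**The concern.** The stated error and power describe one test, and the plan has four candidates for it. It does not say which score carries the efficacy question, in what order the scores are tested, or how many must be significant. Scheffé's method handles contrasts that follow a significant result within one outcome. It does nothing about error across outcomes.

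Two things are at stake. First, if the results are read in the usual way, with any significant primary score taken as a signal, the chance of a false signal exceeds 0.05 by an amount the plan neither states nor limits. Second, the lead score could be chosen after the data are seen, and the 0.90 power has no defined referent.

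**Working it through.** **Inputs from section 2.3.** d = 0.80; variance ratio VR = 0.44; type I error 0.05; power 0.90; 1:1 allocation; 40% attrition. Sidedness is not stated.

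**1. Reproduce the plan's sample size.** For one two-sided test,

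n per arm = 2 × VR × (z₀.₉₇₅ + z₀.₉₀)² / d² = 2 × 0.44 × (1.960 + 1.282)² / 0.64 = 14.45, so 15 per arm and 30 in total.

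With attrition, 30 / (1 − 0.40) = 50. Both figures match the plan. A one-sided test gives 24 in total and omitting the variance ratio gives 66; neither matches. The arithmetic is right, and it is the arithmetic of one test.

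**2. Count the primary scores.** The COPM gives two and the YC-PEM gives two, hence four. The count is read from the scoring text; the plan labels instruments and not scores. Desire for change is also asked on the YC-PEM, but it is given no total score.

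**3. Chance of at least one false positive at 0.05 each.** This assumes no true effect on any score and that any one significant score counts as success. The documents give no correlation between the scores, so a range is shown (simulated normal test statistics with a common correlation).

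| Scores tested | Assumed correlation | Chance of at least one |
|---|---|---|
| 4 | 0 | 1 − 0.95⁴ = 18.5% |
| 4 | 0.3 | 17.4% |
| 4 | 0.5 | 15.6% |
| 4 | 0.7 | 13.0% |
| 4 | 0.9 | 9.4% |
| 4 | 0.7 within, 0.3 between instruments | 15.5% |
| 2 (one per instrument) | 0 | 1 − 0.95² = 9.75% |

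**4. Power if all four stay primary.** Holm's first step tests at 0.05/4 = 0.0125. With the noncentral t distribution, ncp = 0.80 / √(2 × 0.44/15) = 3.30 on 28 df:

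- 15 per arm: per-score power is 0.89 at 0.05 and 0.73 at 0.0125. The normal approximation gives 0.91 and 0.79.
- 25 per arm, with d and variance unchanged: ncp = 4.26 on 48 df, and power at 0.0125 is about 0.95.

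To keep 0.90 per score at 0.0125, the normal formula needs 20 per arm, or 40 evaluable, and 40/0.60 = 66.7, so 67 recruited (68 for equal arms).

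**5. What the 0.44 appears to refer to.** Under compound symmetry with correlation r, the mean of three measurements adjusted for one baseline has variance ratio (1 + 2r)/3 − r². This is largest at r = 1/3, where it equals 4/9 = 0.44, which fits the conservative assumption described in section 2.3. One time point adjusted for one baseline has ratio 1 − r², which is 0.89 at r = 1/3. Then ncp = 0.80 / √(2 × 0.889/15) = 2.32, and power with 15 per arm is about 0.61. The normal formula gives 29.2, so 30 per arm and 60 evaluable. At assumed r of 0.5, 0.6 and 0.7 the power is 0.69, 0.75 and 0.84.

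**The case against.** The strongest reply is that the plan never claims family-wise control. Section 2.3 attaches 0.05 to one ANCOVA, and each single test nominally keeps that level. This stands. A reader might infer that the design fails to have its stated type I error, and the documents do not support that. What is missing is any statement of the error attached to the primary efficacy conclusion.

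A reader might also infer that any one significant score will count as efficacy, or that such a result will be used to launch the next trial. Neither is written. Section 2.8 gives no decision rule, and the only success criteria fixed in advance are the feasibility criteria in Table 1. If all four scores had to be significant, the error would be at most 0.05. That rule is not written either, and the 0.90 would not be the power of that joint requirement.

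Finally, this is a pilot concerned with feasibility, acceptability and initial efficacy. That lowers the severity. It does not close the gap, because the sample size rests on a formal efficacy test, a significance threshold is set, and the p-values are nowhere called exploratory.

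**Conclusion.** The point holds in a limited form. The sample size is correct for one two-sided test, and the plan does not say which of four primary scores that test concerns. On an any-one-counts reading, the chance of a false primary signal is roughly two to four times 0.05: 18.5% for four independent scores and 9.4% at a correlation of 0.9. These figures rest on three assumptions: that reading of success, the count of four, and the correlations tried. Counting one score per instrument still gives 9.75% if the two are independent.

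**What to change.** Name one score, for example COPM performance, analysed with the planned repeated-measures ANCOVA over the planned time points, as the primary efficacy test to which 0.05 and 0.90 apply. Report the other three as supportive, with the effect sizes and 95% confidence intervals already planned and no claim of significance. This is a change of wording only: 30 evaluable and 50 recruited are unchanged.

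Do not restrict the named test to a single time point without restating power. If 0.44 belongs to the three-measurement average, as it appears to, power at 15 per arm would be about 0.61 at r = 1/3.

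If all four scores must stay primary, use Holm across them and state the first-step per-score power: about 0.73 with 15 per arm, or about 0.95 if all 25 per arm are analysed and d and the variance are unchanged. The second figure is relevant because section 2.8 plans intention-to-treat with the last assessment carried forward, so the number analysed may be closer to 25 per arm than to 15.
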